**Figure 3: Timeline for Intervention Development, Implementation, and Evaluation**

Study Months	Development						Intervention and Evaluation																													
	Year 1						Year 2												Year 3																	
	1	2	3	4	5	6	7	8	9	10	11	12	13	14	15	16	17	18	19	20	21	22	23	24	26	28	30	32	34	36						
Formative research	█																																			
Develop Content	█																																			
Program Website	█																																			
Test Usability	█																																			
Activate HI-QUIT							X																													
Enroll Practices	█																																			
HI-QUIT Available*	█																																			
Patient Exit Cards (H1) †							█						█																							
Web Activity (patient/provider) (H2)							█						█																							
Patient Telephone Follow-up (H3) ‡							█						█																							
End of Project Surveys and Qualitative Interviews																									█											
Hypothesis Testing, Manuscripts	█																																			

\* Available for 21 months for each practice, with monthly updates  
 † Patients recruited in 3 cohorts at Intervention Time 0 (I0), I0 + 6 months, I0 + 12 months  
 ‡ Telephone Follow-up: Tobacco users from website – cessation assessed at 6 months (with cotinine validation)

Although HI-QUIT is heavily focused on enhancing Refer, the intervention has the potential for impact across the 5As. To further clarify, Figure 4 depicts flow of a single example practice and patient over time.

**Figure 4: How HI-QUIT will improve processes of care (5As) and increase smoking cessation – use of the clinical microsystem intervention over time by One example practice and One patient.**

- A1: ASK** – Refer2Quit sends email prompts to hygienists reminding them of the importance of smoking cessation, hygienist downloads printable chart stickers, etc. to increase systematic screening.
- A2: ADVISE** – Refer2Quit materials provide additional knowledge to hygienist on strong advice, dentist/hygienist advises patient.
- A3: ASSESS** – Hygienist explains content of Decide2Quit and assesses willingness of patient to use system, and to Quit.
- A4: ASSIST** – Patient agrees to be recruited and hygienist uses Refer2Quit to directly refer. Decide2Quit sends email reminders to the patient. Patient uses system and talks to family because of the motivational messages.

## D2. The Intervention – HI-QUIT

The intervention for HI-QUIT will be accessed through two portals: Refer2Quit designed for hygienists and Decide2Quit designed for patients. The components of HI-QUIT are described in Figure 5 below (supporting detail is provided in Appendices). We will work with the Internet Programming Lab in the UAB Division of Continuing Medical Education to program these components. This lab is responsible for the programming for [name] and [name]’s prior web-delivered Interventions including DTC.Net. The Lab has also programmed the “Smoking Coach” patient website. The linking of these components is the major innovation of this study. The goal is to close the loop within the clinical microsystem between the patient, provider and processes. By developing components that have 1) active prompts to continued use (email reminders) and 2) are simple to use and thus easily integrated with other processes of care, we hypothesize that the use of both the patient and provider components will be multiplied by integration.

[figure not shown]
### 1. Hygienists’ Portal - Refer2Quit:

The core of the Refer2Quit hygienist portal is a Secure Sockets Layer (SSL) encrypted web form where providers can enter patient’s emails into the system if they agree to be referred. Although we anticipate that hygienists will drive this intervention, dentists will also be able to access the intervention website. The form will be designed to be easily completed by hygienists or front office staff as the patient is discharged from the visit. The Refer2Quit component is targeted to providers. To maximize the use of Refer2Quit, we will supplement the component with supportive sub-modules designed to prompt providers to use the system and maximize their smoking cessation activities.

The Practice Toolbox is patterned after a series of successful Internet-delivered provider interventions including [name] previous Chlamydia Screening intervention, and more so, the current DTC.Net intervention (see Appendix A). Reviewers can access this current website at [www.oralcancerprevention.org](http://www.oralcancerprevention.org). To login, you will be asked to enter a first and last name, use firstname = nih and lastname = reviewer.

### 2. Patients’ Portal - Decide2Quit:

The Decide2Quit patient intervention website will include previous self-management content developed and evaluated for “Smoking Coach” (current HI-QUIT control website) and will also undergo considerable augmentation to be integrated into the microsystem. The major augmentation to transform the “Smoking Coach” into Decide2Quit is the database linkages with Refer2Quit (provider portal), the automated email messaging, the administrative portal for content management. We will also add new content including the latest pharmacotherapies, new “How to Talk to Your Provider” content, and additional risk

Principal Investigator/Program Director (Last, First, Middle): DPBRN c/o [name]

calculators. We envision Decide2Quit as a portal to smoking cessation information. Thus, we will add links to other high-quality web-based information on smoking cessation such as **smokefree.gov**, and will provide links to community resources, heavily emphasizing the additional benefit of quitlines (1-800-Quit-Now).

[figure not shown]
**Help Desk:** In addition to the technical aspects of the system, our recruitment and retention staff will serve as a “help desk.” The help desk will respond to provider and patient questions, but will also be **pro-active**. Interventions that are easier to integrate into the processes of the clinical microsystem are more likely to be adopted. Top-Down, one-size-fits-all interventions often are not well integrated. We plan to be flexible and provide support to intervention microsystems in their implementation of HI-QUIT. Thus, we will work with offices to understand how each practice can best implement active referrals.

### D3. The CONTROL – information prescriptions to refer to patients

#### 1. Hygienist Control – Information Prescriptions

In planning this proposal, we considered several potential controls as suggested by the framework for evaluating complex

interventions. In DTC.Net, we are currently using a wait-list control group. Control providers will have access to the full intervention after data collection is complete. Thus, control hygienists are delivering “usual care.” However, for this intervention, we felt that a wait-list control ignores other recent advances in provider referrals to self-management in smoking cessation (i.e.: information prescriptions).

Also, although we have not had differential attrition in the wait-list control, compared with intervention, in DTC.Net, anecdotally, control providers have expressed concerns about having “nothing new” to provide to patients. We are concerned about the threat of long-term wait-listing to overall retention in the control group. Specifically, we want to test the uniqueness of the integration clinical microsystem intervention. After consideration, we have chosen a more active, symmetric control reflecting recent offline research into provider referrals. Thus, our control group provides parallel interventions – for providers and then patients – that are *not* integrated.

We have chosen an “information prescription” control. Providers in the control group will be provided preprinted pads of “information prescriptions” with their office information, motivational messages for patients, a space for the provider to sign, and the control website address.

The information prescription pads also have an important role in our analysis. The pads will have numbered leave-behind receipts used to tally the number of referrals issued. These pads will be collected from the control practices to obtain an accurate account of the number of patients referred. The control group will not have access to 1) HI-QUIT Help Desk, 2) Refer2Quit portal at the point of care; 2) Feedback Reports of patient activity; 4) automated email reminders for patients and providers; 5) HI-QUIT content updates and linking functions.

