#### **D4. Maximizing the Intervention - Programming, and Usability Testing**

As noted in our task list, the majority of the effort in this project will be devoted to the randomized trial, with recruitment, retention, data collection, and analyses being the major tasks. We have begun to develop conceptual mock-ups of the Refer2Quit portal. *The goal of the referral portal is to be used within the flow of dental care, so the portal must be highly accessible and require minimal data entry. Currently, we plan to only ask hygienists to log into the system and enter the patients email address; that is the only data entry and should take less than one minute.* However, implementing the Internet-delivered intervention will require some refinement of both the content and programming. As noted, content upgrades are critical to engagement and we plan to continuously improve both the patient and provider sites as the study progresses using the following phases:

[figure not shown]
1. Hardware and software for programming. The technological foundation of the intervention will be updated as the Internet evolves. Under the direction of [name], the programming will be developed and maintained by the UAB Continuing Medical Education (UAB CME) web development lab. The UAB CME web lab has four graduate level computer science students at all times and two half-time graphic designers. Currently, our study team uses Windows NT server; Active Server Pages (ASP) server application; Ultra Dev 4; Adobe Photoshop; and Oracle databases for data collection. We will alpha-test the program using multiple web browsers and various bandwidths to avoid cross-platform issues in accessing the intervention. The encryption of content is critical and needs of HIPAA compliance will be carefully tested.

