Because not all smokers will be interested or ready to be referred, we have estimated the number of smokers per practice that will participate in the website over time. We estimated 1,000 visits by unique patients per year to the dental practice. Based on tobacco use prevalence in DTC.Net, approximately 20% of the patients will be smokers. To be conservative, we assume that we will have only two providers per practice actively participating in the intervention. Using these numbers, we have estimated the number that will

Principal Investigator/Program Director (Last, First, Middle): DPBRN c/o [name] participate per practice yearly (Table 8). In many practices, there will likely be more than one hygienist referring. Thus, the actual number referred may be proportionately higher in each arm.

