proportion who QUIT (H3) are assessed continuously throughout the study. For H2, the numerator is the number who GO, as tracked by HI-QUIT and the control website. The denominator is the number referred. Because of the nature of the Internet versus paper referral system, by definition, the continuous assessment of the number of patients who are referred is different by study arm. Our interest in H2 is the proportion of patients referred who logon, or ‘GO’, to the website (% who go = number who visit/number referred). In the intervention group, the webserver collects the number of patients entered into the system per practice (i.e.: denominator, the number referred). In the control group, patients are not entered into an electronic system, but are referred using an “information prescription.” In both groups, the intervention and control websites collect the number of patients who visit the site. Thus, assessment of the numerator is the same, but assessment of the denominator is systematically different by arm. We have developed protocol for more accurately measuring the denominator and the number referred in the control group by using the information prescription pads with a leave-behind notation of when the patient was referred. We will collect the empty prescription pads from the control practices to assess the number of patients referred for the denominator.

For H3, the dependent variable is point prevalent cessation (QUIT). Smoking cessation trialists have recommended assessment of smoking cessation in randomized trials using both measures of 1) point

Principal Investigator/Program Director (Last, First, Middle): DPBRN c/o [name]

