Data Definitions for H2: The primary dichotomous outcome will be whether or not each referred patient goes to the website. The number who visit will be recorded by the website itself which links each visitor to their provider at login. The number referred is continuously registered directly for intervention practices and can be obtained by referral receipts for control practices (see description of information prescriptions and main outcomes above). The analysis will again be done at the patient level with adjustment for clustering within practices.

Analysis for H2: A significant challenge for this hypothesis is how to count the number of patients referred (the denominator) from control practices. For intervention practices, patients will be directly referred into the HI-QUIT system by the providers using Refer2Quit. Thus, for these HI-QUIT intervention practices, we can construct a proportion (number who GO/those who are Referred) using webserver data. However, we have chosen a control to represent a current innovation in referrals, the “information prescription.” Thus, patients will not be logged into the system and we cannot use the system to create a proportion. To calculate the denominator for the control practices, we will use the leave-behind receipts from the control “information prescription” pads to tally the number of referrals from each practice. This will allow us to calculate an exact proportion.

The main patient-level analysis will again use logistic regression to model the probability that a referred smoker goes to the website where the independent variable is the group assignment of their referring practice. Because each website links patients back to their practice, we will again use GEE methods to account for clustering within practices. The main hypothesis will be tested by whether the coefficient for treatment assignment is significant in the model corrected for clustering.

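### The control denominator for H2 and H3 counts slips, with no rule for repeat referrals, so a control smoker referred twice counts twice but can GO or QUIT only once

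*Protocol*

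**What the plan says.** **Control arm.** D3 (Hygienist Control – Information Prescriptions) states: "The pads will have numbered leave-behind receipts used to tally the number of referrals issued". The next sentence treats the tally as a count of people: "These pads will be collected from the control practices to obtain an accurate account of the number of patients referred". D8 adds that the pad carries "a leave-behind notation of when the patient was referred". The only receipt contents described are a number and this notation.

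**Intervention arm.** D8 states: "In the intervention group, the webserver collects the number of patients entered into the system per practice". D4 describes the data entry: "we plan to only ask hygienists to log into the system and enter the patients email address".

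**Use of the counts.** The footnote to Table 10 attaches these two sources to the denominators of both GO and QUIT. The H3 text in D9 says its denominator is the one used in H1, but Table 10 gives H1 the exit-card smokers. Table 10 and the 24 and 48 referrals per practice in D10 show that H3 uses the referral counts. D8 says the GO numerator is patients who visit the site, and QUIT is one status per patient at six months.

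**Precision claimed.** D9 (Analysis for H2) says of the receipts: "This will allow us to calculate an exact proportion". The secondary-analysis paragraph that follows considers lost, damaged or mis-used pads. It says much of that error would undercount the control denominator, and so regards the estimate as conservative.

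**Planning basis.** The text around Table 8 states: "We estimated 1,000 visits by unique patients per year to the dental practice". Table 8 and D10 thus allow each person one referral. D9 and D10 put access at 20 months, and the footnote to Figure 3 at 21. No rule for a second referral of the same smoker appears.

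**The concern.** Slips issued and patients referred are the same number only if nobody is referred twice. Dental patients can return within 20 months. The H1 exit-card item asks about a referral at today's visit, so a practice that refers at every visit will issue repeat slips. Each repeat adds one to the control denominator and cannot add to the numerator. The recorded control GO and QUIT proportions then fall with no change in patient behaviour, and this would happen even if both arms referred exactly the same people.

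The only denominator error whose direction the protocol discusses runs the opposite way. Because the receipt is described without anything that identifies a patient, repeats could not be removed afterwards. This has to be settled when the pads are printed, since no analysis plan can recover persons from unkeyed slips.

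**Working it through.** **Inputs from the protocol.** Referred patients per practice: 24 control, 48 intervention (Table 8, D10). Control GO 20%. Control QUIT among referred 2%. ICC 0.05 for H2 and 0.017 for H3. Two-sided α 0.05. Practices with follow-up: 30 to 40 per arm (D5).

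**Input not in the protocol.** r, the mean number of slips per referred control patient. It is an assumption here and is varied.

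**Reproducing the plan's rates.** Table 8: 4.8/24 = 20% GO. Table 11: 24 × 40 = 960 referred, and 20/960 = 2.08% QUIT. Both reproduce and both assume r = 1.

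**Effect on the recorded rates.** Recorded control rate = true rate / r.

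| r | Control GO (true 20%) | Control QUIT (true 2.08%) |
|---|---|---|
| 1.1 | 18.2% | 1.89% |
| 1.25 | 16.0% | 1.67% |

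If the planned 40% v 20% is real, it is recorded as 40% v 16% at r = 1.25. The odds ratio rises from (0.4/0.6)/(0.2/0.8) = 2.67 to (0.4/0.6)/(0.16/0.84) = 3.5.

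**False rejection when the true rates are equal.** With K practices per arm and ICC ρ:

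- n_I = 48K / (1 + 47ρ)
- n_C = 24rK / (1 + (24r − 1)ρ)
- rejection = Φ((d − 1.96·SE0)/SE1) plus the opposite tail, where d is the recorded difference, SE0 the pooled and SE1 the unpooled standard error.

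H2 at r = 1.25, K = 40:

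- n_I = 1920/3.35 = 573.1 and n_C = 1200/2.45 = 489.8.
- Recorded rates are 0.20 and 0.16, so d = 0.04. The pooled rate is 0.1816, SE0 = 0.02372 and SE1 = 0.02353.
- (0.04 − 1.96 × 0.02372)/0.02353 = −0.276, and Φ = 0.391.

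H3 at r = 1.25, K = 40, true 2% in both arms:

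- n_I = 1920/1.799 = 1067.3 and n_C = 1200/1.493 = 803.8.
- Recorded rates are 0.020 and 0.016, with SE0 = 0.00626 and SE1 = 0.00616.
- The upper tail is Φ(−1.34) = 0.090, and both tails together give 0.094.

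| r | H2, K = 40 | H2, K = 30 | H3, K = 40 |
|---|---|---|---|
| 1 | 5% | 5% | 5% |
| 1.06 | 7% | 7% | 5% |
| 1.1 | 11% | 10% | 6% |
| 1.13 | 16% | 13% | 6% |
| 1.25 | 39% | 31% | 9% |

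If the control effective size is held at its value for 24 patients, the H2 figure at r = 1.25 and K = 40 is 37%.

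**What r might be.** As an illustration only, take the protocol's 12% as an independent chance of referral at each of V visits. Then r = 0.12V/(1 − 0.88^V), which is 1.06 at V = 2, 1.13 at V = 3 and 1.20 at V = 4. Smokers who accept once may accept again more readily, which would raise r.

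**Offset from lost slips.** A loss of 1 − 1/r cancels the effect: 9% of slips at r = 1.1 and 20% at r = 1.25.

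**The case against.** **The asymmetry is partly inferred.** No sentence says repeat e-mail entries are collapsed in the intervention arm, and row 17 of Table 6 speaks of the number of referrals in both arms. A reader might infer that the plan fixes a persons-per-person ratio in one arm and a persons-per-slip ratio in the other. The documents do not go that far. If repeats were counted in both arms, the asymmetry would shrink. What stands is that the control count is described in slips, the intervention record has a key that could remove repeats, and neither arm has a rule.

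**Lost slips act the other way.** A reader might infer a net bias towards the intervention. That is not established: only the direction of the repeat-slip component is.

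**The protocol has safeguards.** D8 and D9 acknowledge that the denominator is assessed differently by arm. D9 adds an H2 analysis of the number who GO per practice and an H3 analysis with GO as the denominator, and neither uses slips. These are real checks, and a positive H2 caused only by repeat slips should not reappear in the first. They are secondary, however, and address different quantities, while the primary tests use slips.

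**The size is unsourced.** The same formula gives 84% for H2 at r = 1.5, but under independent 12% referral that r needs about eight visits per smoker, and nothing in the protocol supports it. Larger H3 figures follow from assuming 4% quitting in both arms, which is not the protocol's control rate. If the planned 40% v 20% is real, H2 power is so high that the decision would not change, only the estimate.

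**Receipt layout may be operational detail.** The full layout is not shown. Even so, D9 claims an exact proportion from what is described.

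**Conclusion.** The point holds in limited form. As written, the primary H2 and H3 analyses divide persons by slips in the control arm, with no patient key described and no rule for repeats. Repeat slips lower the control rates, and the protocol's remark about conservative error does not cover that direction. The count is not shown to be exact.

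The size rests on r, which the documents do not give. For r between 1.06 and 1.25, true GO of 20% in both arms, ICC 0.05, 40 practices per arm and no lost slips, false rejection of H2 runs from about 7% to 39%. For H3 at 2% and ICC 0.017 it is about 6% at r = 1.1 and 9% at r = 1.25, so H2 is the main exposure. These figures also take each intervention patient as counted once, which the text implies but does not state. The change is worth making before pads are printed, because the error cannot be undone afterwards.

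**What to change.** - Define the H2 and H3 denominators as unique patients at first referral, in both arms.
- Add a first/repeat mark to each control receipt. Treat a blank as a first referral in the main analysis and as a repeat in a sensitivity analysis.
- In the intervention arm, count each e-mail address once per practice.
- Report the all-referrals result in both arms as a sensitivity analysis.
- In D9, replace the claim of an exact proportion, and limit the statement about conservative error to lost or damaged pads.

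The cost is one mark on a pad and a few lines in the analysis, with no identifier added. The downside is small: the mark depends on staff or patient recall, some will be wrong, and it adds a recording step in the control arm only.

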#### 2. Patient Control

With the paper information prescriptions, control hygienists will refer patients to Decide2Quit website. Screen shots are included in Appendix C. The webserver will tally the number who “GO” to the website. Again, control group patients will **not** be referred electronically and they will **not** have access to: 1) HI-QUIT Help Desk; 2) automated email reminders for patients; 3) HI-QUIT linking functions.

